5.2. STUDY ARMS AND INTERVENTION

The study will include a single arm.. Participants will undergo the following intervention and procedures:

- Examination of the gingiva and periodontal pockets and study measurements recording – the following measurements will be taken: pocket probing depth, bleeding index, recession level, clinical attachment level, mobility grade and furcation. Additionally, sub-gingival biofilm samples may be taken from some participants periodontal pockets for the purpose of bacterial testing to quantify three main periodontal pathogens: *Porphyromonas gingivalis*, *Tannerella forsythia* and *Treponema denticola*. Samples will be tested at the periodontal clinic by the investigator or his/her assistants, using a BANA-Zyme test kit (OraTec Corp., USA).
- 1-4 sessions of scaling and root planing (SRP) on the entire mouth.
- Dividing the mouth into segments (split-mouth) – one/two segments (quadrants) that will be treated with Pocket-X Gel following SRP and two/three segments (quadrants) that will not undergo any further treatment beyond SRP. The number of treated segments and untreated segments will be decided by the investigators and is dependent on the clinical symmetry between the contralateral segments of each participant.
- 1-2 prophylaxis and oral hygiene instruction sessions.
- 1-3 sessions of treatment with Pocket-X Gel, which will be applied to periodontal pockets present in one/two of the pre-determined mouth segment(s) – administration will be performed by applying the product into the periodontal pockets, through a thin plastic tip attached to a syringe containing Pocket-X Gel. More information regarding Pocket-X Gel administration can be found under section No. 5.3 of this protocol.

Section 5.5 of this protocol provides information regarding the interventions and procedures that will be performed at each study visit.

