5. STUDY DESIGN

5.1. OVERALL DESIGN

This study is a single arm, open-label, split-mouth study.

All enrolled participants will initially undergo root planing and scaling on the entire mouth. Following the completion of scaling and root planing, each participant will have one/two of his/her mouth segments (quadrants) treated with Pocket-X Gel. The contralateral segment(s) of the Pocket-X Gel-treated segment(s) will serve as control.

The study hypothesis is that patients treated with Pocket-X Gel following scaling and root planing will exhibit better periodontal pocket healing on their treated segment(s) than their untreated segment(s) as well as compared to data available in the literature concerning the efficacy of scaling and root planing.

The total duration of the study for each participant will be 6-7 months. The study will include a total of 5-7 visits, depending on the number of scaling and root planing sessions required,

based on the severity of each participant's periodontal disease. Follow-up visits will occur 4, 12 and 24 weeks after completion of scaling and root planing and first application of the studied device. Detailed description of each visit is provided under section 5.5 – Visits and Follow-Ups.

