5.3. METHOD OF ADMINISTRATION

Pocket-X Gel will be applied to the periodontal pockets in the pre-determined mouth segments of study participants, by means of a pre-filled syringe bearing a thin plastic tip, provided by Pocket-X Gel's manufacturer. The syringe tip will be inserted into each periodontal pocket and Pocket-X Gel will be applied until the pocket is completely filled by

the product. Each syringe will contain 1 ml of the product. A maximum of 1 syringe will be used on 1 patient per session. Each syringe is intended for use on a single patient but may be used on multiple periodontal pockets of the same patient at each treatment session. In total, a maximum of 3 syringes will be used on each patient throughout the study. The product's syringe and tips will be discarded after use.

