5.5. VISITS AND FOLLOW-UPS

Participants will enroll into the study after undergoing screening and signing an informed consent form. The study will include 4-7 visits, depending on the amount of sessions required for scaling and root planing. A list of the interventions and procedures that participants will undergo during each visit as well as visit schedule is presented in table 1 below. Further details regarding study interventions and procedures can be found under section 5.2 of this protocol.

Table 1 – Study visits plan

Visit No.	Procedure/Intervention	Schedule
Visits 1-4	
Physical examination, obtaining samples from periodontal pockets for bacterial testing [optional] and recording of study measures.Scaling and root planing on the entire mouth.Dividing the mouth into segments, with one/two segments designated to undergo treatment with Pocket-X Gel throughout the study, and two/three that will not undergo any treatment beyond SRP.Single administration of Pocket-X Gel to each periodontal pocket in the pre- determined segment(s), after completion of scaling and root planing.Instructions on maintaining proper oral hygiene.	Week 0 – Week 4

Follow-up 1	
Physical examination, obtaining samples from periodontal pockets for bacterial testing [optional] and recording of study measures.Single administration of Pocket-X Gel to each periodontal pocket in the pre- determined segment(s) [optional].Instructions on maintaining proper oral hygiene (if further instructions are needed).	4 weeks following completion of scaling and root planing and first product application (\pm 14 days)
Follow-up 2	
Physical examination, obtaining samples from periodontal pockets for bacterial testing [optional] and recording of study measures.Single administration of Pocket-X Gel to each periodontal pocket in the pre- determined segment(s)[optional].	12 Week following completion of scaling and root planing and first product application (\pm 14 days)
Follow-up 3	
Physical examination, obtaining samples from periodontal pockets for bacterial testing [optional] and recording of study measures.	24 Week following completion of scaling and root planing and first product application (\pm 14 days)

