6. STUDY POPULATION

6.1. INCLUSION CRITERIA

In order to be found eligible to participate in this study, an individual must meet all of the following criteria:

1. Provision of signed and dated informed consent form
2. Male or female, aged 18 and above
3. Provision of up-to-date full mouth periapical x-rays
4. Participants suffering from active moderate to severe chronic periodontitis with at least 3 sites of periodontal pockets of 5 mm or greater depth in each quadrant.
5. Participants with a minimum of 6 teeth with periodontal pocket depth of more than 5 mm.
6. Participants with a minimum of 20 teeth

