15. STATISTICAL ANALYSIS

15.1. SAMPLE SIZE CONSIDERATION

The rationale for sample size was based on demonstrating a difference in change in pocket depth between the tested segments and the control, reflecting effect size of 0.5 with 80% power and 5% significance level.

Effect size is defined as the difference in change between the treatments adjusted to standard deviation, and calculated as follows:

$$\frac{(\text{Change from baseline in Test segments} - \text{Change from baseline in Control segments})}{\text{Common standard deviation of the change}}$$

Sample size Justification *

A sample size of 27 will have 80% power to detect an effect size of 0.5 using a Paired t-test with a 0.05 one-sided significance level.

Assuming ~20% dropout rate, 34 subjects will be recruited, in order to have 27 participants who complete the study.

Reference:

* Additional sample size justification presents the same sample size and effect size, but specifies the expected changes within each treatment and the common standard deviation:

A sample size of 27 will have 80% power to detect a difference in means of -0.5 (e.g. a First condition mean, μ_1 , of 2.0 and a Second condition mean, μ_2 , of 2.5), assuming a standard deviation of differences of 1.0, using a paired T-test with a 0.05 one-sided significance level.

The calculations are summarized in the table below:

	1	2
Test significance level, α	0.05	0.05
1 or 2 sided test?	1	1
First condition mean, μ_1	2.0	
Second condition mean, μ_2	2.5	
Mean difference, $\mu_d = \mu_1 - \mu_2$	-0.5	
Standard deviation of differences, σ_d	1.0	
Effect size, $\delta = \mu_d / \sigma_d$	0.5	0.5
Power (%)	80	80
N	27	27

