15.2. STATISTICAL METHODS

Study Population:

Intent-to-treat (ITT) population – all patients enrolled to the study who received at least one treatment.

Per Protocol (PP) population - all patients in the ITT population who completed the study according to the protocol and with no major protocol violations.

General

All measured variables and derived parameters will be listed individually and, if appropriate, tabulated by descriptive statistics. For categorical variables, summary tables will be provided giving sample size, absolute and relative frequency and 95% CI (Confidence Interval) for proportions by study arm. For continuous variables, summary tables will be provided giving sample size, arithmetic mean, standard deviation, median, minimum and maximum and 95% CI (Confidence Interval) by study arm for means of variables.

All tests will be two-tailed, and a p-value of 5% or less will be considered statistically significant.

The data will be analyzed using the SAS ® version 9.3 (SAS Institute, Cary North Carolina).

Periodontal pockets treated with Pocket-X Gel will be analyzed vs.control pockets.

Efficacy assessment

The following efficacy parameters will be summarized in appropriate tables by treatment and visit. Changes from baseline will be summarized as well.

- Pocket probing depth
- Bleeding index
- Recession level
- Clinical attachment level
- Mobility grade
- Furcation
- Specific periodontal bacteria quantification [optional]

The Paired T-test or Signed rank test for two means (paired observations) (as is appropriate) will be applied for analyzing the calculated changes by time point within each treatment.

The Paired T-test or Signed rank test for two means (paired observations) (as is appropriate) will be applied for analyzing the difference in the above measurements and changes between the treatments.

Responder will be defined based on improvement of gingival healing and natural sealing of periodontal pockets. Chi-square test or Fisher's Exact test (as is appropriate) will be applied for comparing the proportion of responders between the tested and the control segments.

The efficacy results will be compared also to literature data, if available. The two-sample T-test or Non-parametric Wilcoxon-Mann-Whitney Rank sum test for independent samples (as is appropriate) will be applied for comparative analysis.

Safety assessment

Safety assessments will be based on Adverse Events (AEs) and oral inspections recorded at each visit.

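### The plan gives no random or other rule for which side of a contralateral pair receives the gel, so side choice can follow baseline depth or prognosis

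*Combined protocol and SAP*

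**What the plan says.** - **Control.** Section 5.1: "The contralateral segment(s) of the Pocket-X Gel-treated segment(s) will serve as control". It describes the study as open-label and split-mouth.
- **Choice of segments.** Section 5.2: "The number of treated segments and untreated segments will be decided by the investigators", a decision that "is dependent on the clinical symmetry between the contralateral segments of each participant". No tolerance for symmetry is given.
- **Designation.** Section 5.3 says the gel "will be applied to the periodontal pockets in the pre-determined mouth segments of study participants". Table 1 in section 5.5 divides the mouth, "with one/two segments designated to undergo treatment with Pocket-X Gel throughout the study". Baseline recording is listed in the same Visits 1-4 block, but the table does not say which comes first or who names the side.
- **Entry floor.** Section 6.1 requires "at least 3 sites of periodontal pockets of 5 mm or greater depth in each quadrant".
- **Analysis.** Section 15.1 sizes the trial on "demonstrating a difference in change in pocket depth between the tested segments and the control". In section 15.2 a paired t-test or signed rank test "will be applied for analyzing the difference in the above measurements and changes between the treatments". No baseline covariate is named.

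**The concern.** Pairing within a mouth removes differences between patients. It does not remove differences between the two sides of a mouth, and here the side is what gets allocated.

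If the side is chosen with baseline readings in view, the choice can follow pocket depth, access, anatomy or expected healing. Change scores cancel a constant difference in starting level. They do not cancel a tendency of deeper pockets to change more. Section 15.2 also compares the measurements themselves, where a baseline side difference enters in full.

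If the deeper side tends to get the gel, and deeper pockets improve more, the comparison favours the gel; if the shallower side does, it works against the gel. Either way, a reader could not separate a gel effect from a side-choice effect.

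**Working it through.** **1. What the text fixes.**

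| Place | Fixes | Leaves open |
|---|---|---|
| 5.1 | Control is the opposite quadrant | Which of the two is treated |
| 5.2 | Who decides the number of segments, and that it depends on symmetry | Side; limit on asymmetry |
| 5.3, Table 1 | The side is set before application and kept throughout | How, by whom, and whether before or after baseline readings |
| 6.1 | A minimum number of deep sites in each quadrant | Any limit on the difference between sides |
| 15.2 | Paired test of changes | Any baseline adjustment |

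**2. The plan's own figure (section 15.1).** Effect size 0.5, one-sided 5%, paired t-test. Power = P(T > critical value), with T noncentral t, df n−1, noncentrality 0.5√n. This gives 0.798 at n = 26 and 0.812 at n = 27, so 27 is reproduced. 27/(1−0.20) = 33.75, which rounds up to 34.

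**3. Bias at a given average imbalance.** From the plan: n = 27, SD of differences 1.0 (15.1), two-tailed 5% (15.2). Assumed, because the documents give neither: slope b = 0.3 to 0.7 mm more reduction per mm of baseline depth, and average imbalance m (gel side deeper). No true gel effect.

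Bias = b × m. Rate of falsely finding the gel better = P(T > 2.056), df 26, noncentrality bias × √27.

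| m (mm) | Bias (mm) | Falsely finds gel better |
|---|---|---|
| 0 | 0 | 2.5% |
| 0.1 | 0.03 to 0.07 | 3.5 to 5.4% |
| 0.3 | 0.09 to 0.21 | 6.6 to 18.2% |

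**4. What imbalance is plausible.** Suppose left-right differences are normal with mean 0 and SD s, and the deeper side is treated with probability p. Then m = (2p−1) × s × √(2/π), where √(2/π) = 0.798.

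- An m of 0.3 mm needs s = 0.3/0.798 = 0.38 mm if the deeper side is always treated, or 0.3/(0.5 × 0.798) = 0.75 mm if treated in 75% of patients. Larger values are unlikely if the symmetry condition works.
- Partial selection with s = 0.3 to 0.5 mm and p = 0.60 to 0.75: m runs from 0.2 × 0.3 × 0.798 = 0.05 mm to 0.5 × 0.5 × 0.798 = 0.20 mm. Bias runs from 0.3 × 0.048 = 0.01 mm to 0.7 × 0.199 = 0.14 mm.

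**5. Simulation of partial selection** (40,000 runs per cell, n = 27, SD of differences held at 1.0, no true effect, ranges over s and b above):

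| Deeper side treated | Falsely finds gel better, planned test | Total two-tailed error, planned test |
|---|---|---|
| 50% (random) | about 2.5% | about 5% |
| 60% | about 3 to 5% | about 5 to 6% |
| 75% | about 4 to 10.5% | about 5 to 11% |

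The upper ends need slope 0.7 and left-right SD 0.5 mm together. Regressing the difference in change on the difference in baseline depth and testing the intercept kept the rate of falsely finding the gel better near 2.5% in every cell. That model has selection on measured depth only and a linear relation.

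**6. The opposite direction.** With a true 0.5 mm effect, two-tailed power at n = 27 is 70.6%. A bias of 0.14 mm against the gel leaves 0.36 mm, and power falls to 43.7%. (The 70.6% rather than 80% arises because 15.1 sizes a one-sided test and 15.2 plans two-tailed ones; that is a separate point.)

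**7. Can adjustment replace a random side?** Two-tailed power of the adjusted test at a true 0.5 mm effect: about 69 to 74% with a random side, about 61 to 67% if the deeper side is treated in 75% of patients, and about 32 to 35% if it is always treated, because equal baseline then lies at the edge of the data.

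**The case against.** The strongest case against has four parts.

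- **Absence is hard to prove.** Some pages were not available, including whatever lay between sections 10 and 12. This stands as a limit on the claim. Sections 5.1 to 5.5, where a side rule would normally sit, are present and silent.
- **The quoted sentence concerns number, not side.** This stands. A reader might infer that the protocol lets investigators put the gel on whichever side they prefer, or that they will pick the deeper one. The documents say neither. The point rests on omission.
- **The bias is assumed and may be small.** Slope, imbalance and selection probability all come from outside the documents, and under partial selection total error is only about 5 to 11%. A reader might take the 18.2% figure, or a bias towards the gel, as what to expect. The documents do not support that: direction is unknown and the symmetry condition argues against large imbalance. But these figures cover selection on measured depth only. Selection on unmeasured prognosis is not bounded by them.
- **Missing covariate adjustment is not a defect in itself.** This stands. With a random side the planned test holds its 5% error and adjustment changes power little.

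**Conclusion.** The concern holds as a gap in allocation. In the available text, nothing determines which side of a pair receives the gel, and the comparison on which the trial is sized depends on that choice. Symmetry, the entry floor and change scores are partial safeguards; none fixes the side or makes the sides equal.

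Under the assumed slopes and partial selection, bias is 0.01 to 0.14 mm against a target difference of 0.5 mm. The documents do not show that results will be biased, or in which direction. They show that the design offers no protection, and that analysis afterwards can correct only for what was measured. That is reason enough to settle the side rule before any further side is assigned.

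**What to change.** 1. **Sections 5.1, 5.2 and Table 1.** State that the gel side is assigned from a pre-generated, concealed random list (for example sealed, numbered envelopes). It is opened only after the investigator has decided which contralateral pair or pairs qualify and whole-mouth scaling and root planing is complete. Use one draw per patient, left or right, applied to all qualifying pairs. Separate draws for two pairs could put gel and control quadrants on the same side. If a rule already exists elsewhere, write it into these sections.
2. **Section 15.2.** Keep the paired test as the main between-treatment analysis, on one mean per condition (gel, control) per patient. As a pre-specified sensitivity analysis only, regress the within-patient difference in change on the within-patient difference in baseline depth, uncentred, so that the intercept is the gel effect at equal baseline.
3. **Participants already assigned, if any.** The documents do not say whether enrolment has begun. Identify anyone whose side was set before the change and report them separately as non-randomised by side. State that baseline adjustment corrects only for measured depth and is imprecise if the deeper side was nearly always treated.

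**Cost.** A list and envelopes, loss of investigator discretion over side (not over which pairs qualify), and a protocol amendment that may need renewed approval under section 1. The 27 completers and 34 recruited are unchanged, and the sensitivity analysis uses baseline values that section 9.1 already collects.

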5.3. METHOD OF ADMINISTRATION

Pocket-X Gel will be applied to the periodontal pockets in the pre-determined mouth segments of study participants, by means of a pre-filled syringe bearing a thin plastic tip, provided by Pocket-X Gel's manufacturer. The syringe tip will be inserted into each periodontal pocket and Pocket-X Gel will be applied until the pocket is completely filled by

the product. Each syringe will contain 1 ml of the product. A maximum of 1 syringe will be used on 1 patient per session. Each syringe is intended for use on a single patient but may be used on multiple periodontal pockets of the same patient at each treatment session. In total, a maximum of 3 syringes will be used on each patient throughout the study. The product's syringe and tips will be discarded after use.

5.4. NUMBER OF PARTICIPANTS

A total of approximately 34 participants will be included in the study, taking into account 20% dropout/lost to follow-up, thus allowing complete data collection from a sufficient number of participants to make a reliable assessment.

5.5. VISITS AND FOLLOW-UPS

Participants will enroll into the study after undergoing screening and signing an informed consent form. The study will include 4-7 visits, depending on the amount of sessions required for scaling and root planing. A list of the interventions and procedures that participants will undergo during each visit as well as visit schedule is presented in table 1 below. Further details regarding study interventions and procedures can be found under section 5.2 of this protocol.

Table 1 – Study visits plan

Visit No.	Procedure/Intervention	Schedule
Visits 1-4	
Physical examination, obtaining samples from periodontal pockets for bacterial testing [optional] and recording of study measures.Scaling and root planing on the entire mouth.Dividing the mouth into segments, with one/two segments designated to undergo treatment with Pocket-X Gel throughout the study, and two/three that will not undergo any treatment beyond SRP.Single administration of Pocket-X Gel to each periodontal pocket in the pre- determined segment(s), after completion of scaling and root planing.Instructions on maintaining proper oral hygiene.	Week 0 – Week 4

Follow-up 1	
Physical examination, obtaining samples from periodontal pockets for bacterial testing [optional] and recording of study measures.Single administration of Pocket-X Gel to each periodontal pocket in the pre- determined segment(s) [optional].Instructions on maintaining proper oral hygiene (if further instructions are needed).	4 weeks following completion of scaling and root planing and first product application (\pm 14 days)
Follow-up 2	
Physical examination, obtaining samples from periodontal pockets for bacterial testing [optional] and recording of study measures.Single administration of Pocket-X Gel to each periodontal pocket in the pre- determined segment(s)[optional].	12 Week following completion of scaling and root planing and first product application (\pm 14 days)
Follow-up 3	
Physical examination, obtaining samples from periodontal pockets for bacterial testing [optional] and recording of study measures.	24 Week following completion of scaling and root planing and first product application (\pm 14 days)

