3.2. STUDIED DEVICE

The studied device, Pocket-X Gel, manufactured by Israeli-based Tree of Life Pharma Ltd., is an *in-situ* gelling device, used as physical barrier against bacterial re-colonization of the periodontal pockets following root surface debridement or scaling and root planing. Pocket-X Gel is provided in a pre-filled syringe along with 2 tips. It is applied to the periodontal pocket by a dentist using the provided syringe bearing one of the tips. It is applied in the form of a liquid, which transforms into a gel once placed in the periodontal pocket, due to contact with body temperature. The gel fills the periodontal pocket and prevents bacterial infiltration into the pre-cleaned pocket. One syringe can be used for multiple periodontal pockets present in the mouth of the same patient. The syringe or tip cannot be used on a different patient.

Pocket-X Gel contains the following components: Water, Poloxamer 407, Hyaluronic Acid, Phenoxyethanol, Octenidine Dihydrochloride.

The device is biodegradable. It remains within the periodontal pocket for a period of 1-3 weeks, afterwards it is either degraded or ejected from the pocket following natural sealing of the pocket as part of the gums healing process.

Pocket-X Gel only contains materials that are commonly used in oral products and are considered safe for oral use based on available literature. Additionally, *in-vivo* animal experiments conducted with the product at a GLP-certified laboratory indicated no irritation or sensitization. It is therefore expected that treatment with Pocket-X Gel will present a high safety profile during the study.

Furthermore, the product's application in the form of a liquid and its transformation into a gel only after its application allows to the product to perfectly fit the pocket's dimensions and shape. In addition, the product is applied through a thin and flexible plastic tip that does not traumatize the surrounding tissues. It is therefore expected that the product and its administration process will cause no discomfort to the patient.

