9. STUDY ASSESSMENTS

9.1. EFFICACY ASSESSMENT

The following measurements will be recorded during the study, and will be used to assess the efficacy of the intervention:

- Plaque index
- Pocket probing depth
- Bleeding index
- Recession level
- Clinical attachment level
- Mobility grade
- Furcation
- Specific periodontal bacteria quantification [optional]

The above measurements will be recorded at baseline and at follow-up visits for each participant. The values will be recorded separately for each periodontal pocket. .

Efficacy data from follow-up visits will be compared to the baseline values in order to obtain the efficacy results. The efficacy results will be compared between treated periodontal pockets and control periodontal pockets and to data obtained from available literature.

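### The 14-day tolerance lets follow-up 1 fall on days 14-21, when gel may still be in test pockets but not in controls; exposure is probably small and easily removed

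*Combined protocol and SAP*

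**What the plan says.** Section 5.5, Table 1, times follow-up 1 at "4 weeks following completion of scaling and root planing and first product application". The tolerance follows directly: "first product application (\pm 14 days". Follow-ups 2 and 3, at weeks 12 and 24, carry the same tolerance.

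On how long the gel stays, section 3.2 says: "It remains within the periodontal pocket for a period of 1-3 weeks". After that it is degraded or ejected. Section 5.3 describes the application: "Pocket-X Gel will be applied until the pocket is completely filled by" the product. Table 1 describes the remaining segments as "two/three that will not undergo any treatment beyond SRP".

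On measurement, section 9.1 says: "The above measurements will be recorded at baseline and at follow-up visits for each participant". It also says that values are kept separately for each pocket. Section 5.2 makes bacterial testing selective: "sub-gingival biofilm samples may be taken from some participants periodontal pockets".

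On analysis, section 15.2 says: "The following efficacy parameters will be summarized in appropriate tables by treatment and visit". It then provides paired tests of the difference between treatments.

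The supplied text contains no instruction to look for or clear residual gel before probing, and no rule for an early follow-up 1. The text available for review passes from section 10 to section 12, so anything between them could not be checked.

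**The concern.** A split-mouth comparison relies on test and control pockets being measured under the same conditions on the same day. If follow-up 1 takes place while gel is still present, one side of the pair is probed with material in the pocket and the other without. Pairing within the mouth cannot remove that difference, because it lies between the two sides.

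The readings at stake are the week-4 clinical measures, probing depth among them, and the optional bacterial samples in those participants who give them. Section 15.1 sizes the trial on change in pocket depth without naming a visit, and section 15.2 names no primary visit. Follow-up 1 is therefore not set apart from the main test-versus-control comparison.

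**Working it through.** **Inputs.** Nominal follow-up 1: 4 weeks = day 28 (Table 1). Tolerance: 14 days either way (Table 1). Residence: 1-3 weeks = days 7-21 (section 3.2). Completers: 27 (section 15.1). The plan's own inflation for dropout reproduces: 27 / (1 - 0.20) = 33.75, rounded up to 34. That figure is not in dispute; 27 serves here only as a scale.

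**Step 1, the overlap.** The window runs from 28 - 14 = day 14 to 28 + 14 = day 42, which is 29 whole days. Residence ends by 3 x 7 = day 21. The overlap is days 14-21, which is 8 of the 29 permitted days. The nominal day 28 is clear by 7 days.

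**Step 2, the later visits.** These are checked for the case where gel is re-applied at the preceding follow-up.
- Follow-up 1 to 2, shortest gap: (84 - 14) - (28 + 14) = 70 - 42 = 28 days.
- Follow-up 2 to 3, shortest gap: (168 - 14) - (84 + 14) = 154 - 98 = 56 days.

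Both exceed 21 days, so only follow-up 1 is exposed.

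**Step 3, how often gel would be present.** The documents give neither the spread of visit days nor the distribution of residence, so both are assumed and varied.
- Visit day V: either normal about day 28 with SD 3, 5 or 7 days, taken on whole days and truncated to 14-42, or even over the 29 days.
- Residence R: either uniform over days 7-21, so P(R > v) = (21 - v)/14 for v from 14 to 21, or clustered late (uniform over days 14-21), so P(R > v) = (21 - v)/7.
- Expected exposure, scaled to 27: 27 x sum over v of P(V = v) x P(R > v).

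Worked case, even spread: the sum of (21 - v) over days 14 to 21 is 7 + 6 + ... + 0 = 28. Then 28 / (29 x 14) = 0.069, and 27 x 0.069 = 1.86. With late residence, 28 / (29 x 7) = 0.138, and 27 x 0.138 = 3.72.

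| Visit spread | P(visit on days 14-21) | Scaled to 27, residence 7-21 | Scaled to 27, residence 14-21 | P(visit on days 14-20) |
|---|---|---|---|---|
| SD 3 | 0.015 | 0.02 | 0.04 | 0.006 |
| SD 5 | 0.095 | 0.32 | 0.64 | 0.065 |
| SD 7 | 0.164 | 0.78 | 1.56 | 0.13 |
| Even | 8/29 = 0.276 | 1.86 | 3.72 | 7/29 = 0.24 |

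These figures are expected shares of test-pocket readings, expressed on a scale of 27. Reading them as numbers of participants needs the further assumption of one residence time per mouth.

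**Step 4, which lower limit clears the overlap.** 28 - 7 = day 21, which touches the stated maximum. 28 - 6 = day 22, which is past it. In both residence models P(R > 21) = 0, so a limit of -7 already removes all modelled overlap, and -6 additionally clears day 21 itself.

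**The case against.** The strongest reply is that this is a calendar overlap with no demonstrated consequence. Nothing in the documents says that residual gel alters a reading of depth, attachment or bleeding. That stands: the point concerns a difference in measuring conditions, not a proven error.

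The second reply is that the overlap would rarely occur. Five of the six scenarios centred on day 28 give an expected exposure below one of 27, and the even spread ignores the fact that clinics aim for the nominal day. That also stands, and it keeps the point minor.

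The third is that gel leaves pocket by pocket. Some test pockets in a mouth may hold gel while others do not. The number of participants with any gel could then be higher than the table suggests, and the effect on each participant's mean smaller. This is a fair limit on how the figures are read.

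The fourth is that a narrower window could turn visits that now comply into deviations and shrink the per-protocol set, since section 15.2 does not define a major violation. This carries less weight. That set excludes only major violations, and a visit a few days early would ordinarily be a minor one.

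None of these replies removes the overlap itself, which follows from two figures that the plan states.

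**Conclusion.** The point holds as a minor one. The plan permits a compliant follow-up 1 on days 14-21, when by its own account gel may remain in test pockets and cannot be in control pockets. On the assumed visit spreads and residence shapes, the expected exposure is about 0.02-1.6 of 27 if visits centre on day 28, and 1.9-3.7 of 27 if they spread evenly.

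A reader might infer more in two ways, and the documents support neither:
- **That the week-4 comparison is biased for or against the gel.** No direction or size of effect on probing can be derived from the text, so no figure in millimetres is claimed.
- **That about 28% of readings, or roughly 7 of 27, are affected, because 8 of 29 days overlap.** That requires visits spread evenly over the window and gel lasting through day 21 in every test pocket (27 x 8/29 = 7.4). The plan aims for day 28 and states residence as a range that starts at one week.

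The finding that no rule covers early visits applies only to the supplied text.

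**What to change.** In Table 1, change the follow-up 1 window from 14 days either side to -6/+14 days, that is, days 22-42. This clears the stated three-week maximum. A window of -7/+14 days is nearly equivalent and is enough under the assumed models; the choice depends on how literally the end of week three is taken. No extra analysis and no change to the analysis sets is needed.

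The cost is some scheduling freedom. The window shrinks from 29 to 21 whole days (22 at -7). On the assumed spreads, about 1.5%, 9.5%, 16% or 28% of follow-up 1 visits would be booked later, by at most 8 days (22 - 14). At -7 the shares are about 0.6%, 6.5%, 13% or 24%. Visits before the new limit would become minor schedule deviations. The nominal day 28, follow-ups 2 and 3, the number of gel sessions and the sample size stay as they are.
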